Protocol for observational studies based on existing data

Document Number:	c03412460-01
BI Study Number:	1160-0235
BI Investigational Product(s):	Dabigatran etexilate (Pradaxa®)
Title:	Pradaxa Initiation Post-Stroke Study: SITS-Pradaxa 1. A retrospective analysis from the SITS-AF Registry on treatment initiation of dabigatran etexilate in non-valvular atrial fibrillation patients hospitalized with acute ischemic stroke
Lay Title	This study uses the SITS Registry to find out when patients with a heart rhythm disorder (atrial fibrillation) start treatment with dabigatran after they had a stroke
Protocol version identifier:	1.0
Date of last version of protocol:	05 July 2017
PASS:	No
EU PAS register number:	EUPAS17165
Active substance:	B01AE07 - dabigatran etexilate (Pradaxa®)
Medicinal product:	Dabigatran etexilate
Product reference:	EU/1/08/442/001-019
Procedure number:	EMA/H/C/000829
Joint PASS:	No
Research question and objectives:	
Primary Objective:
 
 To evaluate the timing of dabigatran treatment initiation in patients with non-valvular atrial fibrillation (NVAF) after hospitalization for first ever ischaemic stroke (the index event) in order to prevent secondary stroke. 
Secondary Objectives:
 
 To describe baseline characteristics for patients

Protocol for observational studies based on existing data

BI Study Number 1160-0235

c03412460-01

Proprietary confidential information © 2017 Boehringer Ingelheim International GmbH or one or more of its affiliated companies

	
treated with dabigatran according to time of dabigatran initiation.
 
 • To describe self-reported factors important for the physician's decision as to the time of dabigatran initiation in the post-ischemic stroke setting. • To describe self-reported factors important for physician's decision as to which dabigatran dose was used in the post-ischemic stroke setting.
Countries of study:	
Data from all patients in European countries* actively registered in the SITS Registry until 31 July 2018, will be considered for analysis.
 
(*countries such as, Italy, United Kingdom, Czech Republic, Sweden, Germany, Poland, Spain, Finland, Portugal, Slovakia, Denmark, Estonia, Norway Belgium, Hungary, Slovenia, Croatia, Austria, Lithuania, France, Greece, Netherlands, Ireland, Ukraine and Iceland)

Authors:	
E-mail:
 
E-mail:
 
Address:

2. LIST OF ABBREVIATIONS

AE	Adverse Event
AF	Atrial Fibrillation
CHAD ₂ score	Stroke Risk score based on a point system, which includes history of Congestive heart failure, Hypertension, Age (≥ 75), Diabetes mellitus, Stroke/TIA.
CHA ₂ DS ₂ -VASc score	Stroke Risk score based on a point system, which includes history of Congestive heart failure, Hypertension, Age (≥ 75), Diabetes mellitus, Stroke/TIA, Vascular disease, Age 65-74, Sex category
CI	Confidence Interval
EMA	European Medicines Agency
ENCePP	European Network of Centers for Pharmacoepidemiology and Pharmacovigilance
EUPAS	The European Union electronic Register of Post-Authorisation Studies (EU PAS Register)
GVP	Good Pharmacovigilance Practices
HAS-BLED	Bleeding Risk score based on a point system, which includes Hypertension, Abnormal renal and liver function, Stroke (1 point), Bleeding history or predisposition, Labile INR, Elderly (>65 years), Drugs and Alcohol
ICO	International Coordinating Office (at SITS International)
IEC	Independent Ethics Committee
INR	International Normalized Ratio
IRB	Institutional Review Board
LV EF	Left Ventricular Ejection Fraction
MAH	Marketing authorisation holder
MI	Myocardial Infarction
mRS	modified Rankin Scale
N.A.	Not applicable
NIHSS	National Institute of Health Stroke Scale
NOAC	Non-vitamin K Oral Anticoagulation
NVAF	Non-valvular Atrial Fibrillation
OAC	Oral Anticoagulant
p.o.	per os (oral)
PASS	Post-Authorisation Safety Study
q.d.	quaque die (once a day)
SITS	Safe Implementation of Treatment in Stroke (Registry)
SITS-MOST	Safe Implementation of Thrombolysis in Stroke-Monitoring Study
SmPC	Summary of Product Characteristics
TCM	Trial Clinical Monitor
TIA	Transient Ischaemic Attack
t.i.d.	ter in die (3 times a day)
TMF	Trial Master File
TMM	Team Member Medicine
VKA	Vitamin K Antagonist

4. ABSTRACT

Name of company: Boehringer Ingelheim			
Name of finished medicinal product: Pradaxa			
Name of active ingredient: Dabigatran etexilate			
Protocol date: 05 July 2017	Study number: 1160-0235	Version/Revision: 1.0	Version/Revision date: N.A.
Title of study:	Pradaxa Initiation Post-Stroke Study: SITS-Pradaxa 1. A retrospective analysis of existing data from the SITS-AF Registry on treatment initiation of dabigatran etexilate in non-valvular atrial fibrillation patients hospitalized with acute ischemic stroke		
Rationale and background:	
Dabigatran etexilate (Pradaxa) is the first non-VKA oral anticoagulant (NOAC) for stroke prevention in non-valvular atrial fibrillation (NVAF) patients. Compared with warfarin, dabigatran 150 mg twice daily exhibited lower rates of stroke and systemic embolism, but similar rates of major haemorrhage; whereas treatment with dabigatran 110 mg twice daily showed similar rates of stroke and systemic embolism, but lower rates of major haemorrhage. Both dosages of dabigatran etexilate were associated with lower rates of intracranial haemorrhage.
 
Dabigatran has been approved in most countries worldwide including Europe and US to reduce the risk of stroke and systemic embolism in patients with NVAF. In addition, the results from the RE-LY study concerning the use and outcome of anticoagulant therapy with dabigatran in NVAF patients have been confirmed in routine clinical practice data. In RE-LY, severe, disabling stroke within the previous 6 months, or any stroke within the previous 14 days was excluded and therefore, data in the acute setting on secondary stroke prevention is sparse.
 
The initiation of warfarin for the secondary prevention of ischemic stroke in NVAF has been established over the years of its use and is based on the severity of the index event. It ranges between 2-3 days for TIA up to 3-4 weeks for large ischemic
		

Protocol for observational studies based on existing data

BI Study Number 1160-0235

c03412460-01

Proprietary confidential information © 2017 Boehringer Ingelheim International GmbH or one or more of its affiliated companies

Name of company: Boehringer Ingelheim			
Name of finished medicinal product: Pradaxa			
Name of active ingredient: Dabigatran etexilate			
Protocol date: 05 July 2017	Study number: 1160-0235	Version/Revision: 1.0	Version/Revision date: N.A.
	
insults. For dabigatran the time ranges of initiation after the index event have not yet been established.
 
Therefore, the aim of this study is to explore the current use of dabigatran etexilate for stroke prevention in NVAf patients in the post-stroke setting in routine clinical practice.
 
In this study, the SITS Registry the entered data of approximately 1000 eligible patients, that initiated dabigatran after the index event, will be extracted for retrospective analysis.
		
Research question and objectives:	
Primary Objective:
 
 To evaluate the timing of dabigatran treatment initiation in patients with non-valvular atrial fibrillation (NVAf) the after hospitalization for first ever ischaemic stroke, in order to prevent secondary stroke. 
Secondary Objectives:
 
 To describe baseline characteristics for patients treated with dabigatran according to time of dabigatran initiation. To describe self- reported factors important for the physician's decision as to the time of dabigatran initiation in the post-ischemic stroke setting. To describe self- reported factors important for physician's decision as to which dabigatran dose was used in the post-ischemic stroke setting. 		

Protocol for observational studies based on existing data

BI Study Number 1160-0235

c03412460-01

Proprietary confidential information © 2017 Boehringer Ingelheim International GmbH or one or more of its affiliated companies

Name of company: Boehringer Ingelheim			
Name of finished medicinal product: Pradaxa			
Name of active ingredient: Dabigatran etexilate			
Protocol date: 05 July 2017	Study number: 1160-0235	Version/Revision: 1.0	Version/Revision date: N.A.
Study design:		This is a retrospective observational study using existing data from the SITS registry	
Population:		NVAF patients presenting with their first ever ischemic acute stroke.	
Variables:		
 • Patient characteristics such as age, stroke severity based on NIHSS, selected comorbidities, CHADS₂, CHA₂DS₂-VAS_c and bleeding (HAS-BLED) risk scores, prior oral anticoagulation treatment (dabigatran, Factor Xa Inhibitors, VKA) at index stroke date, the timing of dabigatran treatment initiation for secondary prevention of stroke when initiated within 3 months. • Physicians' self-reported factors important for their decisions when to initiate dabigatran in the post-ischemic stroke setting and factors important for physician's decision which dabigatran dose is used in the post-ischemic stroke setting for prevention of stroke in NVAF. • 	
Data sources:		SITS-AF Registry data of approximately 1000 dabigatran treated patients in European countries registered in the SITS-AF Registry (expected by 31 st July 2018).	
Study size:		Approximately 1000 NVAF patients who are treated with dabigatran etexilate within 3 months of their first ischemic	

Protocol for observational studies based on existing data

BI Study Number 1160-0235

c03412460-01

Proprietary confidential information © 2017 Boehringer Ingelheim International GmbH or one or more of its affiliated companies

Name of company: Boehringer Ingelheim			
Name of finished medicinal product: Pradaxa			
Name of active ingredient: Dabigatran etexilate			
Protocol date: 05 July 2017	Study number: 1160-0235	Version/Revision: 1.0	Version/Revision date: N.A.
	stroke (index event) constitute the main analysis population.		
Data analysis:	
Descriptive statistics (absolute numbers and relative frequencies, means, standard deviations, medians, inter quartile ranges, minimum and maximum values, 95% confidence intervals and proportions, as appropriate) for baseline and demographic characteristics for all included patients will be provided as appropriate for the variable of interest.
 
The main analysis will focus on NVAF patients presenting with first ischemic acute stroke and treated with dabigatran within 3 months of index event.
 
We will describe the timing of dabigatran treatment initiation for secondary prevention of stroke when treatment is initiated within 3 months in the post-stroke setting.
 
We will summarize the self-reported factors (i.e. as collected in the Registry using a dedicated question) important for the physician's decision for the timing when to initiate dabigatran and the self-reported factors important for which dabigatran dose is used in the post-ischemic stroke setting for prevention of stroke. Descriptions will also be stratified according to time of dabigatran initiation if sample size allows.
 
Dabigatran patients will be described stratified by timing of dabigatran treatment initiation, newly diagnosed NVAF or prevalent NVAF, prior treatment with anticoagulation including type of anticoagulation therapy, stroke severity measured by
		

Protocol for observational studies based on existing data

BI Study Number 1160-0235

c03412460-01

Proprietary confidential information © 2017 Boehringer Ingelheim International GmbH or one or more of its affiliated companies

Name of company: Boehringer Ingelheim			
Name of finished medicinal product: Pradaxa			
Name of active ingredient: Dabigatran etexilate			
Protocol date: 05 July 2017	Study number: 1160-0235	Version/Revision: 1.0	Version/Revision date: N.A.
	NIHSS score, dose of dabigatran, if the sample size allows.		
	Individual patient safety related information will not be captured during this study. Thus, individual safety reporting is not applicable.		
Milestones:	Individual patient data are collected in the SITS-AF Registry since the presentation of 'Extended data entry option for atrial fibrillation and oral anticoagulant', 1 st July 2014. After approximately 1000 dabigatran treated patients from European Centres are registered in SITS-AF (expected by July 2018), the data will be extracted and a retrospective final analysis will be performed.		

5. AMENDMENTS AND UPDATES

Not applicable

Protocol for observational studies based on existing data

BI Study Number 1160-0235

c03412460-01

Proprietary confidential information © 2017 Boehringer Ingelheim International GmbH or one or more of its affiliated companies

6. MILESTONES

Milestone	Planned Date
Start of study/data collection	17 July 2017
End of data collection	31 July 2018 (The time-point when approximately 1000 dabigatran treated patients with completed observation time are expected to be registered in the database and data extraction will be done for the analysis)
Registration in the EU PAS register	13 July 2017 (registration no. EUPAS 17165)
Final report of study results:	31 December 2018 (Considering that the observation time for 1000 dabigatran treated patients is completed by 31 July 2018.)

7. RATIONALE AND BACKGROUND

Stroke is the third most common cause of death in industrialised countries after myocardial infarcts and tumour diseases. [P90-55974] Stroke is also the most common cause of permanent disability. About 85% of all strokes are ischaemic, the remaining part haemorrhagic. One year after a total anterior circulation infarct, 60% of the patients have died and 35% have so severe neurological deficits that independent activities of daily living are restricted. With milder strokes, about 40% die or remain dependent. [R96-0250] Since the incidence of stroke is strongly age-related, the number of stroke victims is expected to increase substantially over the next decades when the proportion of the population over the age of 70 is estimated to grow from about 13% to 20%. Even within the next decade, the number of stroke victims is expected to increase by about 15%. [R17-1269] The burden of stroke is heavy for the victims and for society. The yearly direct and indirect costs for stroke in Europe can be estimated to about 25 billion Euros. Since the stroke incidence is expected to be about 750.000 in ten years, these costs might increase by about 10-15% if we do not succeed to prevent more strokes and improve the effect of acute stroke intervention.

Atrial fibrillation (AF) and stroke

Atrial fibrillation (AF) is the most common arrhythmia and the prevalence of AF is about 0.4 to 1% in the general population, rising to 8% in those subjects over 80 years. [R03-1233, R12-2675, P10-00760] The number of patients with AF is likely to increase 2.5-fold during the next 50 years. [R03-1233] Patients with AF have a 5 fold increased risk of ischemic stroke compared to persons without AF. [R96-0252] AF related strokes are more severe, are more likely to cause disability or to recur, and carry a higher mortality risk than strokes in patients without AF. [R09-4892, R10-0658, R10-0340] Clinical practice guidelines developed by the American College of Cardiology, American Heart Association, European Society of Cardiology, and American College of Chest Physicians recommend that all patients with AF and a CHADS₂ or CHA₂DS₂-VASc score ≥ 2 should receive long-term oral anticoagulation. [P10-10141, P11-03902, P12-01676] In the American College of Chest Physicians and European Society of Cardiology guidelines, oral anticoagulation also is recommended in patients with a CHADS₂ or CHA₂DS₂-VASc score of 1. [P10-10141] Vitamin K antagonists (e.g. warfarin) were the only oral anticoagulants available until 2010 and updated guidelines include the newer oral anticoagulants as alternatives to vitamin K antagonists for stroke prevention. [P11-03902, P12-01676, P11-03903, P17-04650]

Anticoagulation treatment in patients with AF for stroke preventions

Long-term anticoagulation treatment reduces the incidence of ischemic stroke in patients with AF. In a meta-analysis, adjusted-dose warfarin reduced the risk of stroke by 64% compared to placebo and by approximately 40% compared to antiplatelet therapy. [P07-07953] Warfarin treatment is underused, particularly in elderly population and maintaining appropriate anticoagulation levels with warfarin is often difficult because of variable dose responses, multiple drug-drug and drug-food interactions, a slow onset and offset of action. Warfarin-treated patients require routine coagulation monitoring, dose adjustments, and dietary precautions to ensure a balance between therapeutic anticoagulation and bleeding risk.

Protocol for observational studies based on existing data**BI Study Number 1160-0235****c03412460-01**

Proprietary confidential information © 2017 Boehringer Ingelheim International GmbH or one or more of its affiliated companies

Dabigatran, the first new Oral Anticoagulants

Dabigatran etexilate (Pradaxa) is the first non-Vitamin K Antagonist oral anticoagulant (NOAC) for stroke prevention in non-valvular atrial fibrillation (NVAf) patients. Dabigatran, a direct thrombin inhibitor, was evaluated in the phase III Randomized Evaluation of Long-term Anticoagulation Therapy (RE-LY) study. [P09-11669] Compared with warfarin, dabigatran 150 mg twice daily exhibited lower rates of stroke and systemic embolism, but similar rates of major haemorrhage; whereas treatment with dabigatran 110 mg twice daily showed similar rates of stroke and systemic embolism, but lower rates of major haemorrhage. Dabigatran has been approved more than 100 countries world-wide including Europe and US to reduce the risk of stroke and systemic embolism in patients with NVAf.

The European approved current version of Pradaxa® Summary of Product Characteristics (SmPC) can be found on the EMA Webpage:

- <http://ec.europa.eu/health/documents/community-register/html/h442.htm>.

The US approved version of the SmPC can be found on the FDA webpage:

- <https://www.accessdata.fda.gov/scripts/cder/daf/index.cfm?event=overview.process&ApplNo=022512>

Data from clinical studies such as RE-LY and RELY-ABLE [P09-11669, P13-08115] where the safety of dabigatran in stroke prevention has been demonstrated for up to 5 years were confirmed by studies in real world clinical practices in different patient populations. [P14-15648, P15-10687] However, it remains important to continue to address further real world clinical questions, which were so far not assessed in studies.

In RE-LY, severe, disabling stroke within the previous 6 months, or any stroke within the previous 14 days was excluded and therefore, data on the initiation of dabigatran treatment post-ischemic stroke for secondary stroke prevention in NVAf patients is sparse.

The initiation of warfarin for the secondary prevention of ischemic stroke in NVAf has been established over the years of its use and is based on the severity of the index event. It ranges between 2-3 days for TIA to 3-4 weeks for large ischemic insults. For dabigatran these initiation ranges after the index event have not yet been established. Therefore, the aim of this study is to explore the current real world use of dabigatran for stroke prevention in NVAf patients in the post-stroke setting. Therefore data on the timing of dabigatran treatment initiation will be described by analysing data on NVAf patients after hospitalization for acute ischemic stroke in this study.

8. RESEARCH QUESTION AND OBJECTIVES

Primary objective:

- To evaluate the timing of dabigatran treatment initiation in patients with non-valvular atrial fibrillation (NVAF) after hospitalization for first ever ischaemic stroke (the index event), in order to prevent secondary stroke.

Secondary objectives:

- To describe baseline characteristics for patients treated with dabigatran according to time of dabigatran initiation.
- To describe self-reported factors important for the physician's decision as to the time of dabigatran initiation in the post-ischemic stroke setting.
- To describe self-reported factors important for physician's decision as to which dabigatran dose was used in the post-ischemic stroke setting.

Protocol for observational studies based on existing data**BI Study Number 1160-0235****c03412460-01**

Proprietary confidential information © 2017 Boehringer Ingelheim International GmbH or one or more of its affiliated companies

9. RESEARCH METHODS**9.1 STUDY DESIGN**

This is an observational, multinational, multicentre, study in patients with NVAF presenting to a hospital with a first acute ischemic stroke. The study is based on existing data recorded in the SITS International Registry by physicians in European countries, such as Italy, United Kingdom, Czech Republic, Sweden, Germany, Poland, Spain, Finland, Portugal, Slovakia, Denmark, Estonia, Norway Belgium, Hungary, Slovenia, Croatia, Austria, Lithuania, France, Greece, Netherlands, Ireland, Ukraine and Iceland. All patients with NVAF will be included that present with the first ever ischemic stroke. For these patients baseline and demographics variables are available such as medical history including comorbidities and concomitant medications. Characteristics will further be used to estimate common stroke (CHADS₂, CHA₂DS₂-VAS_c) and bleeding (HAS-BLED) risk scores. Details on NVAF and secondary stroke prevention: time since first diagnosis, prior anticoagulation treatment, dose, and stroke severity of index event measured by National Institute of Health Stroke Scale (NIHSS) score, are recorded in the registry.

For patients that receive dabigatran within 3 months of the index event, details on post-stroke treatment (time from hospital admission – start and dose of dabigatran treatment for stroke prevention in NVAF, concomitant medication) will be analysed. Variables for physician's decision when to initiate oral anticoagulation with dabigatran post-ischemic stroke and the dose selected will be analysed.

In addition any start/stop of dabigatran treatment and doses prescribed will also be assessed at discharge and at 3 months after the index event.

9.2 SETTING

Patients with NVAF presenting with their first ever acute ischemic stroke who are registered in the SITS International Registry from 1 July 2014 until approximately 31 July 2018 will be included in the study.

Inclusion criteria

- Patients with non-valvular Atrial Fibrillation (NVAF)
- Patients presenting with their first acute ischemic stroke
- ≥ 18 years of age

Exclusion criteria

- Documentation that the patient was enrolled or is planned to be enrolled in an investigational clinical trial at the time of the onset of the index event and for the duration of the data collection

Protocol for observational studies based on existing data

BI Study Number 1160-0235

c03412460-01

Proprietary confidential information © 2017 Boehringer Ingelheim International GmbH or one or more of its affiliated companies

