9.3.2 Outcomes

9.3.2.1 Primary outcomes

- The time lapsed from the index event to the initiation of the dabigatran treatment. This will be further categorized in specified time periods.

The following time periods will be considered, but could be revised (e.g. merging categories) depending on sample size 0-24h, >24-72h, >3-7d >7-14d, >14-28d, >28d-3m.

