9.3.2.2 Secondary outcomes

- Description of baseline characteristics for patients treated with dabigatran according to time of dabigatran initiation.
- Description of self-reported factors important for physician's decision when to initiate dabigatran in the post-ischemic stroke setting for prevention of stroke and safety in NVAf.
- Description of self-reported factors important for physician's decision which dabigatran dose is used in the post-ischemic stroke setting for secondary prevention of stroke and safety in NVAf.

Definitions

Ischemic stroke is defined as an event characterised by sudden onset of acute focal neurological deficit (e.g. resulting in an impairment of speech, motor function, cognition, gazes, vision, and/or neglect) presumed to be caused by cerebral ischemia/infarction after exclusion of haemorrhage by imaging scans.

The index event is the date of first ever ischemic stroke.

The 3 month follow-up data point for patients is 90 (+/- 10) days after the index event.

Major intracranial haemorrhage is defined as symptomatic intracranial bleeding at any time after start of dabigatran treatment and within 3 months from index event.

The evaluation of intracranial haemorrhage will be done using the available CT/MRI scan after start of dabigatran treatment and within 3 months from index event.

Major extracranial haemorrhage is derived from safety documentation in the SITS registry.

Death is defined as all cause death.

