6.1 Primary Analysis

This analysis will be done for NVAF patients presenting with first ischemic acute stroke and treated with dabigatran within 3 months of index event.

To describe the distribution of dabigatran treatment initiation times in patients with non-valvular atrial fibrillation (NVAF) after hospitalization for first-ever ischemic stroke (the index event) treated with dabigatran, we will

1. Create a histogram of initiation times by day.
2. Calculate mean, standard deviation and 95% (Standard Normal) confidence intervals (CI) of the Mean, as well as the median, interquartile ranges, minimum and maximum values.
3. Create frequency table by time periods. Give the absolute count of subjects and the proportion of subjects in each group. The time periods to be considered are 0-24h, >24-72h, >3-7d >7-14d, >14-28d, >28d-3m, however these categories may be revised depending on the distribution of initiation times to ensure sufficient patient numbers in each category.

We do not expect to have any missing values in the time to dabigatran treatment initiation. However, if there are missing values collected, they will be summarized in the frequency table as a separate category. Proportions for all other categories will not include the missing values in the denominator (as this is what has been done in previous works for all previous SITS-MOST and/or SITS-ISTR publications [P07-00880, P08-11746].). The proportion of missing values will be out of all subjects sampled.

6.2 Secondary Analysis:

These analyses will be done for NVAF patients presenting with first ischemic acute stroke and treated with dabigatran within 3 months of index event.

6.2.1 To describe baseline characteristics for patients treated with dabigatran according to time of dabigatran initiation.

Descriptions will only be done for the subgroups (of time to initiation) consisting of at least 100 patients. We Will:

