▪ Warfarin derivatives
▪ New OAC (NOAC)
• If NOAC
○ Dabigatran
○ Apixaban
○ Rivaroxaban
2h follow up
Systolic Blood Pressure
Diastolic Blood Pressure
NIHSS
24h follow up
NIHSS
Systolic Blood Pressure
Diastolic Blood Pressure
Current Infarct CT/MR
ASPECTS Score CT/MR
Local Haemorrhage CT/MR
Remote Haemorrhage CT/MR
Cerebral Oedema CT/MR
At discharge/ 7d
Diagnosis of NVAf at (previous, at or during hospital stay)
Oral anticoagulation (OAC) at = YES
▪ Warfarin derivatives
▪ New OAC (NOAC)
• If NOAC
○ Dabigatran
○ Apixaban
○ Rivaroxaban
Date & time of OAC start: DD/MM/YYYY, time: clock
OAC at discharge = No
1) Date of foreseen start of OAC if not started during hospital stay
Date: DD/MM/YYYY
Aspirin
mRS Score
NIHSS
Systolic Blood Pressure
Diastolic Blood Pressure
Date of
Dipyridamole
Clopidogrel
Other Antiplatelet

Anticoagulants Oral
Dabigatran
Dabigatran Dose
Date of Dabigatran Initiation
Anti Diabetic Oral
Antihypertensive Oral
Statin
Other
Type Of Stroke
Type Of Stroke Ischemic
Type Of Stroke Haemorrhagic
Date Time Of Death
Cause Of Death
At 3-months
Modified Rankin Scale score
If mRS=6=Dead, date/time of death
Cause of death
Patients with NVAf at discharge/ 7d but patient has not been prescribed Warfarin or NOAC (Dabigatran, Apixaban, Rivaroxaban at
1) Has the patient been prescribed Dabigatran after discharge?
If YES questions below will also be shown.
2) Date of initiation of Dabigatran for stroke prevention in NVAf
Date: DD/MM/YYYY
Dose:
Patients with NVAf has been prescribed dabigatran at discharge
Is the patient continuing the prescribed Dabigatran at 3 months follow up since start of the treatment?
- Yes/ No/ Unknown
If No, date of stop of treatment:
Reason for stop of treatment:
- Has the OAC treatment been changed?
If Yes,
Which treatment:

7.2 Appendix 2

CHADS₂ Stroke Risk Score

CHADS ₂ components	Points
Congestive heart failure	1
Hypertension	1
Age 75 years or older	1
Diabetes mellitus	1
Prior cerebral ischemia (i.e., stroke, TIA)	2
Maximum score	6

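### Patients are admitted up to the planned extraction date with no follow-up condition in the SAP, so the most recent index strokes enter the primary set mainly as in-hospital starters and tilt the start-time distribution towards early starting

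*Protocol*

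**What the plan says.** **Who is admitted.** Protocol 9.2 and SAP 4 take patients "registered in the SITS International Registry from 1 July 2014 until approximately 31 July 2018". The inclusion and exclusion criteria contain no minimum time between index stroke and extraction.

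**When data are cut.** The milestone table in Protocol 6 puts end of data collection, with extraction, at 31 July 2018. It describes that date as "The time-point when approximately 1000 dabigatran treated patients with completed observation time are expected to be registered in the database". The final-report date carries a similar rider: "Considering that the observation time for 1000 dabigatran treated patients is completed by 31 July 2018".

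**Who is analysed.** SAP 6.1 states: "This analysis will be done for NVAF patients presenting with first ischemic acute stroke and treated with dabigatran within 3 months of index event". It requires neither a completed 3-month form nor full potential follow-up.

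**Where late starts are recorded.** In the variable list in SAP Appendix 7.1, the 3-month block asks "Has the patient been prescribed Dabigatran after discharge" and then for the start date and dose. The discharge form holds actual starts up to that point; for anyone not yet started it holds only a foreseen date.

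**When that form is due.** Protocol 9.3.2.2 says: "The 3 month follow-up data point for patients is 90 (+/- 10) days after the index event". SAP 3.1 agrees. The last two start-time categories in Protocol 9.3.2.1 are ">14-28d, >28d-3m", with no day given for the upper limit.

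**The concern.** The primary outcome is the distribution of time from index stroke to first dabigatran, among patients who started within 3 months. Membership of the analysis set therefore depends on the start having been seen. For a stroke in June 2018, an in-hospital start is on file at extraction and the patient counts. If the same patient starts in week five, no form has yet recorded it and the patient does not count. Recent calendar time thus supplies early starts and few late ones.

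This differs from loss to follow-up, because the contact is not missed but not yet due. It always acts in the same direction, and the sponsor can avoid it entirely. SAP 5 attributes selection to death, a second stroke or leaving care, and Protocol 9.9 discusses loss to follow-up. Neither mentions the data cut.

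**Working it through.** There is no planned figure to reproduce: Protocol 9.5 says that the size of about 1000 rests on availability. The check is calendar arithmetic plus a simple dilution formula.

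**1. Length of the window.** 1 July 2014 to 31 July 2018, both included, is 1492 days.

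**2. Index strokes too recent for the 3-month form.** The form may be completed from day 80 to day 100. Counting back from 31 July 2018:

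| Days before extraction | Index date | Share of window, even accrual |
|---|---|---|
| 80 | 12 May 2018 | 80/1492 = 5.4% |
| 90 | 2 May 2018 | 90/1492 = 6.0% |
| 100 | 22 April 2018 | 100/1492 = 6.7% |

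After 12 May no contact is due by extraction. Between 22 April and 12 May some contacts will be complete and some not. So 5.4% and 6.7% are lower and upper bounds under even accrual.

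The documents give no accrual curve. Two assumed alternatives for the last 100 days:
- Linear rise from zero: 1 − (1392/1492)² = 13.0%.
- Doubling yearly: (1 − 2^(−100/365.25)) / (1 − 2^(−1492/365.25)) = 18.4%.

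**3. Effect on the late share.** Let L be the true share of starters who start after discharge (not in the documents, so assumed) and f the fraction of those starts not observable at extraction. In-hospital starts are all seen, so

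observed share = L(1 − f) / (1 − Lf).

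| Assumed L | f = 5.4% | f = 6.7% | f = 13.0% | f = 18.4% |
|---|---|---|---|---|
| 20% | 19.1% | 18.9% | 17.9% | 16.9% |
| 40% | 38.7% | 38.3% | 36.7% | 35.2% |
| 60% | 58.7% | 58.3% | 56.6% | 55.0% |

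Example: 0.40 × 0.933 / (1 − 0.40 × 0.067) = 0.383. Under even accrual the shift is 0.9 to 1.7 points; under the two steeper curves it is 2.1 to 5.0 points.

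**4. Effect on the mean.** Assume mean start times of 4 days for in-hospital starters and 48.5 days for later ones. The mean falls by (L − observed share) × 44.5. For L between 20% and 60% under even accrual this is about 0.4 to 0.75 day.

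**5. Set against the disclosed loss to follow-up.** Protocol 9.9 expects 20% loss at 3 months. Applied alone to post-discharge starters with L = 40%, the observed share is 0.40 × 0.80 / (1 − 0.40 × 0.20) = 34.8%. With f = 6.7% as well, and the two losses assumed independent, it is 33.2%. The loss to follow-up is about three times as large (20/6.7), and the cut-off adds about 1.6 points to it.

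**6. Contact window.** If contacts are spread evenly over days 80-100, a start on day t in that range is seen with probability (100 − t)/20. That is 0.50 at day 90 and 0.75 on average over days 80-90. If starts are also evenly spread over days 28-90, the last category loses 10 × 0.25/62 = 4.0%.

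**The case against.** The best answer is in the milestone table. Protocol 6 ties the 31 July 2018 cut to completed observation twice, which shows that the sponsor meant to analyse fully observed patients. If that were applied as an eligibility rule, the cut-off problem would vanish and only the small contact-window effect would remain. The intent is clear. But the wording states when about 1000 such patients are expected, and it excludes nobody. The abstract's milestones and Protocol 9.5 speak only of patients being registered, and the condition appears in neither Protocol 9.2 nor the SAP.

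Three stronger readings are tempting and are not supported.

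- A reader might infer that recent patients can enter only as early starters. Contacts open at day 80, so patients with strokes between 22 April and 12 May 2018 may already have a completed form.
- A reader might infer that starts on days 91-100 will inflate the last category. The form records a calendar start date, so such starts can be set aside whenever the contact took place.
- A reader might infer a serious distortion. Under even accrual it is not: with 1000 patients the 95% half-width is 2.5 points for a 20% share and 3.0 points for 40%, wider than the shift. That makes the bias modest, though sampling error does not cancel it.

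It is also fair that the study is descriptive, and that SAP 5 already calls its findings conditional on starting treatment and hypothesis generating. That caution does not identify the data cut as a cause.

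**Conclusion.** The point holds as a gap between Protocol 6 on one side and Protocol 9.2, SAP 4 and SAP 6.1 on the other. An analyst following the SAP would retain recent in-hospital starters and miss recent post-discharge starters, so the primary distribution leans towards early starting.

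The size is about 1-2 points on the late share and under one day on the mean if accrual is even. It is roughly 2-5 points under the steeper assumed curves. These figures rest on assumed accrual shapes, an assumed late share of 20-60%, and post-discharge starts being known only from the 3-month form. The effect is smaller than that of the 20% loss to follow-up but falls on the same patients and adds to it. The documents do not show that the sponsor intended to include incompletely observed patients, nor that the primary result would be seriously misleading. The case for acting is that the bias is one-directional and cheap to remove.

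**What to change.** Reconcile Protocol 6, Protocol 9.2, SAP 4 and SAP 6.1 with one stated rule:

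- Limit the primary analysis set to index strokes at least 100 days before extraction, which means on or before 22 April 2018 for a 31 July 2018 extraction; or extract at least 100 days after the last admitted index stroke.
- Define within 3 months as a start on day 0-90 by the recorded date, whatever the date of the contact.
- Note in the limitations that contacts on days 80-89 may miss a few late starts, about 4% of the last category if starts and contacts are evenly spread. A table cut at day 80 is optional.

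**Cost.** The index-date rule removes about 7% of patients under even accrual and up to about 18% under steep accrual, including some from 22 April to 12 May whose contact is already complete. The alternative delays extraction by about 100 days, which would also press on the 31 December 2018 report date. The day 0-90 definition costs one sentence.
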